#### 4.4.2 Secondary Efficacy Analyses

For all the secondary efficacy analyses, no multiplicity adjustment will be made.

- Proportion of subjects with  $\leq 6.0$  mg/dL in SUA level at Week 12 (LOCF)

The difference in responder rate at Week 12 (LOCF) between dotinurad 2 mg and febuxostat 40 mg and the stratified 95% confidence interval will be estimated based on Mantel–Haenszel method adjusting for the baseline SUA level and baseline BMI. The prespecified non-inferiority margin will be  $-10\%$  in this analysis, which will be for the reference purpose only. The number (percentage) of responder and the asymptotic 95% confidence interval at Week 12 (LOCF) (see section 7) will be presented by treatment group.

The same analysis mentioned above will be repeated supplementally based on the PP Analysis Set.

- Proportion of subjects with  $\leq 6.0$  mg/dL in SUA level at each time point

The number (percentage) of responder at each visit (Week 4, Week 8, Week 12, Week 16, Week 20, Week 24) will be presented by treatment group.

Responder rate for each treatment group at each visit (Week 4, Week 8, Week 12, Week 12 (LOCF), Week 16, Week 20, Week 24, Week 24 (LOCF)) will be presented by bar chart.

- Mean percent reduction from baseline in SUA level at each time point

The mean percent reduction from baseline in SUA level at each visit (Week 4, Week 8, Week 12, Week 12 (LOCF), Week 16, Week 20, Week 24, Week 24 (LOCF)) will be summarized by treatment group using descriptive summary statistics. In addition, box-plot will be used for graphical presentation.

The following subgroup analysis will be repeated:

- SUA level category ( $<9$ ; 9 to  $<10$ ; 10 to  $<11$ ;  $\geq 11$  mg/dL)
- BMI category ( $<25$ ;  $\geq 25$  kg/m $^2$ )
- Classification of hyperuricemia (overproduction type, underexcretion type, combined type, other type)

In addition, the mean percent reduction and difference in least squares (LS) means between dotinurad and febuxostat, and corresponding 95% confidence interval will be estimated based

on the mixed-effects models for repeated measures (MMRM). The model will be adjusted for the baseline SUA value, baseline SUA level category (<9; 9 to <10; 10 to <11;  $\geq 11$  mg/dL) and baseline BMI category (<25;  $\geq 25$  kg/m^2), treatment, time (Week 4, Week 8, Week 12, Week 16, Week 20, Week 24) and the interaction of treatment by time. The Kenward-Roger approximation will be used to estimate denominator degrees of freedom. The unstructured covariance matrix (UN) will be used in the analysis. In the case of nonconvergence of UN, the toeplitz covariance matrix (TOEP) will be used. In the case of nonconvergence with TOEP, the autoregressive covariance matrix [AR (1)] will be used in the model. The use of MMRM will be based on the assumption of missing at random (MAR), which means no imputation for missing values will be conducted.

- Mean SUA level and mean change from baseline in SUA level at each time point

The mean actual value and the mean change from baseline in SUA level at each time point (Baseline, Week 4, Week 8, Week 12, Week 16, Week 20, Week 24, Week 24 (LOCF)) will be summarized by treatment group using descriptive summary statistics and presented by box-plot.

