## 2 CLINICAL PROTOCOL SYNOPSIS

Compound No. FYU-981
Name of Active Ingredient: Dotinurad
Study Protocol Title A Randomized, Multicenter, Double-Blind, Superiority Study of Dotinurad (4 mg) and Febuxostat (40 mg) for the Treatment of Subjects With Gout
Sites Approximately 30 sites
Study Period and Phase of Development Approximately 21 months from first subject enrolled to last subject's last visit/last assessment. Phase 3
Objectives Primary Objective To confirm the superiority of dotinurad 4 mg to febuxostat 40 mg on the proportion of subjects achieving a serum uric acid (SUA) level $\leq 6.0$ mg/dL at Week 24 in Chinese subjects with gout. Secondary Objectives 

• To confirm the non-inferiority of dotinurad 2 mg to febuxostat 40 mg on the proportion of subjects achieving a SUA level <math>\leq 6.0</math> mg/dL at Week 12 in Chinese subjects with gout

• To compare the proportion of subjects achieving a SUA level <math>\leq 6.0</math> mg/dL at each time point between treatment groups

• To compare the percent reduction in SUA level from baseline at each time point between treatment groups

• To compare the change in SUA level from baseline at each time point between treatment groups

• To compare the SUA level at each time point between treatment groups

• To evaluate the safety and tolerability of dotinurad

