#### Secondary Efficacy Analyses

For all the secondary efficacy analyses, no multiplicity adjustment will be made.

The difference in the responder rate at Week 12 (LOCF) between dotinurad 2 mg and febuxostat 40 mg and the 95% confidence interval will be estimated based on Mantel–Haenszel method adjusting for the baseline SUA level and baseline BMI. The prespecified non-inferiority margin will be  $-10\%$  in this analysis, which will be for the reference purpose only.

The proportion of subjects with  $\leq 6.0$  mg/dL in SUA level at each time point will be summarized.

The mean percent reduction from baseline in SUA level at each time point will be summarized using descriptive summary statistics (eg, n, mean, SD, median, minimum, maximum), estimated based on the longitudinal data analysis (LDA) model and presented in figures. The detail of the LDA model will be specified in the SAP.

The mean actual value and the mean change from baseline in SUA level at each time point will be summarized using descriptive summary statistics.

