### 7.3.3 Study Duration

Treatment I Phase of 4 weeks is selected to prevent the risk of gouty arthritis caused by a rapid decrease in the SUA level. The duration is based on Japan Phase 3 studies.

Eight-week duration of dotinurad 2 mg/day in Treatment II Phase is based on FYU-981-014 study, which was a Phase 3 study conducted in Japan. In FYU-981-014 study, the duration of 2 mg/day was 8 weeks. And it is sufficiently long for this duration to assess non-inferiority of dotinurad 2 mg and febuxostat 40 mg in Chinese patients. That allows us to compare Chinese data and Japanese data as necessary.

Twelve-week duration of dotinurad 4 mg/day in Treatment II Phase is based on EMA paper on guideline on clinical investigation of medicinal products for the treatment of gout (EMA/CHMP/774470/2018). According to this guideline, the pivotal trials should be sufficiently long to establish a sustained effect of urate lowering for at least 3 months, once the treatment is optimized at a stable dose level. So in this study, 12 weeks of dotinurad 4 mg/day is established.

EMA paper on guideline on clinical investigation of medicinal products for the treatment of gout also suggests that a parallel, randomized, double-blind trial should be performed for a minimum of 6 months. Therefore, subjects in the dotinurad group will be treated for 24 weeks in total.

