**Table 1      Treatments Administered**

	Treatment I Phase (4 weeks)	Treatment II Phase (20 weeks)	
	Day 1 to Day 28	Day 29 to Day 84 (8 weeks)	Day 85 to Day 168 (12 weeks)
Test treatment	Dotinurad 1 mg One dotinurad 1 mg tablet and one febuxostat 20 mg-matched placebo tablet (Except Day 0)	Dotinurad 2 mg One dotinurad 2 mg tablet and two febuxostat 20 mg-matched placebo tablets	Dotinurad 4 mg Two dotinurad 2 mg tablets and two febuxostat 20 mg-matched placebo tablets
Comparator treatment	Febuxostat 20 mg One febuxostat 20 mg tablet and one dotinurad 1 mg-matched placebo tablet (Except Day 0)	Febuxostat 40 mg Two febuxostat 20 mg tablets and one dotinurad 2 mg-matched placebo tablet	Febuxostat 40 mg Two febuxostat 20 mg tablets and two dotinurad 2 mg-matched placebo tablets

The study drug will be administered orally once daily at approximately the same time each day.

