#### 4.3.3 Multiple Comparisons/Multiplicity

Treatment group comparison for the primary efficacy endpoint will be conducted at  $\alpha = 0.05$  (2-sided). No multiplicity adjustments will be performed for other efficacy analyses including sensitivity analysis based on non-responder imputation and supplemental analysis based on PPS.

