**Table 2 Windowing Rules**

Week	Target Visit Date (Study day)	Visit Window (Study day)
Week 24 (LOCF) c d	—	—
End of Treatment e	—	—

- a The last non-missing values including unscheduled assessments on or prior to the date of first dose.
- b The last non-missing values including unscheduled assessments up to Day 98 (inclusive) will be carried forward as the data for the efficacy analysis, which is known as Week 12 (LOCF).
- c The last non-missing values including unscheduled assessments up to Day 182 (inclusive) will be carried forward as the data for the efficacy analysis, which is known as Week 24 (LOCF).
- d For subjects who discontinued the study, the last non-missing values up to 14 days after the date of last dose will be carried forward as the data for the efficacy analysis.
- e The last non-missing values including unscheduled assessments during the study will be used for the safety analysis only.

In case of multiple assessments within the same visit window, the assessment closest to the target visit day will be used in data analyses; in the event of two assessments being equally close to the scheduled visit day, the latest assessment in time will be used. In the event of two assessments being equally close to the scheduled visit day, the data will be considered in an individual case.

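### Week 12 (LOCF) can count a sample taken on dotinurad 4 mg as the 2 mg result: close the window at the first third-period dose, and align the objective to confirm non-inferiority with its reference-only analysis

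*SAP*

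**What the plan says.** **Windows.** Protocol Table 1 gives the dotinurad arm 2 mg on Days 29 to 84 and 4 mg from Day 85. SAP 4.4.2 labels the Week 12 (LOCF) comparison as dotinurad 2 mg against febuxostat 40 mg. SAP Table 2 attaches two footnotes to Week 12 (LOCF). Under footnote b, the last values "including unscheduled assessments up to Day 98 (inclusive) will be carried forward". Under footnote d, for subjects who discontinued, "the last non-missing values up to 14 days after the date of last dose will be carried forward". The observed Week 12 window is Day 71 to 98. Neither the footnotes nor the window mentions the change of dose.

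**Objective and analysis.** The protocol synopsis, Protocol 8.2 and SAP 2.1.2 all give a secondary objective "To confirm the non-inferiority of dotinurad 2 mg to febuxostat 40 mg on the proportion of subjects achieving a SUA level" of 6.0 mg/dL or less at Week 12. Protocol 7.3.3 adds, of the 8-week 2 mg period, that "it is sufficiently long for this duration to assess non-inferiority of dotinurad 2 mg and febuxostat 40 mg in Chinese patients". The analysis sections then give the −10% margin a different status: "which will be for the reference purpose only" in the protocol (synopsis and 9.7.1.6.2), and "in this analysis, which will be for the reference purpose only" in SAP 4.4.2. SAP 4.3.3 reserves alpha for the primary endpoint: "No multiplicity adjustments will be performed for other efficacy analyses".

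**The concern.** A comparison labelled 2 mg should use values measured on 2 mg. LOCF here takes the latest value in the window, not the one nearest Day 84. A later sample on 4 mg therefore displaces a valid scheduled Week 12 sample; it does not merely fill a gap. The febuxostat arm stays on 40 mg across Day 85, so only the dotinurad arm changes active dose inside the window.

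Protocol 7.3.4 supposes that 4 mg might be needed to reach the target in Chinese subjects. On that premise the error is likely to favour dotinurad, and so to favour a non-inferiority reading. The direction is not certain: an early-termination sample taken some days after the last dose may be higher.

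The second issue is one of wording. If the lower confidence limit lies above −10 points, the objective lists invite the word *confirmed*, while the analysis sections support only a descriptive statement. The report's wording should be settled before results are known.

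**Working it through.** **1. The plan's own figure.** Inputs from SAP 3: 45% against 60%, 225 per arm, two-sided 0.05, chi-square test. Power = Φ{[√n·Δ − 1.96·√(2p̄q̄)] / √(p₁q₁ + p₂q₂)} with p̄ = 0.525. That is Φ{(15 × 0.15 − 1.96 × 0.7062) / 0.6982} = Φ(1.240) = 89.3%, which reproduces the stated approximately 90%. No power is stated for Week 12.

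**2. The windows side by side.**

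| Item | Source | Days |
|---|---|---|
| Dotinurad 2 mg | Protocol Table 1 | 29–84 |
| Dotinurad 4 mg | Protocol Table 1 | 85–168 |
| Scheduled Week 12 visit | Protocol Table 3 | 77–91 |
| Delayed increase (unresolved gouty arthritis) | Protocol 9.4.7.4 | up to 91 |
| Observed Week 12 | SAP Table 2 | 71–98, closest to 84 |
| Week 12 (LOCF) | SAP Table 2, footnote b | up to 98, last value |

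Nominal overlap of the LOCF window with 4 mg: 98 − 85 + 1 = 14 days. Day 85 is nominal because visits have a window and the increase can be delayed. A limit tied to the dose change therefore fits better than a fixed calendar day.

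Two hypothetical subjects, each starting 4 mg on Day 85:
- Scheduled sample on Day 84, unscheduled sample on Day 95. Week 12 (LOCF) takes Day 95, a 4 mg value.
- Scheduled sample on Day 77 (7 days from target), unscheduled sample on Day 89 (5 days from target). The closest-value rule for observed Week 12 also takes the 4 mg value, since Table 2 does not exclude unscheduled samples from that window.

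**3. Size of the misclassification (assumptions only).** Let a share f of dotinurad subjects have a 4 mg value counted as 2 mg. Assume a true 2 mg rate of 35% (exactly at the margin against 45%) and a 4 mg rate of 60%, borrowed from the Week 24 assumption. The counted rate is (1 − f) × 35% + f × 60%. The chance that the lower limit clears −10 points is Φ{(p_T − p_C + 0.10)/SE − 1.96}, with SE = √[(p_T q_T + p_C q_C)/225].

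| f | Subjects of 225 | Counted rate | Bias (points) | Chance of clearing −10 |
|---|---|---|---|---|
| 0 | 0 | 35.0% | 0 | 2.5% |
| 2% | 4.5 | 35.5% | 0.5 | 3.2% |
| 5% | 11.25 | 36.25% | 1.25 | 4.6% |
| 10% | 22.5 | 37.5% | 2.5 | 7.8% |

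The documents support no value of f. The 60% may also be too high for someone at most two weeks into 4 mg.

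**4. Power if Week 12 became a formal claim.** Same formula, unstratified, 225 per arm. No Week 12 rate for Chinese subjects is stated, so these are scenarios.

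| Dotinurad 2 mg vs febuxostat | Basis | Power |
|---|---|---|
| 41.8% vs 45% | difference of −3.2 points from the Japanese study, moved to the 45% control rate | 31% |
| 45% vs 45% | equal rates | 57% |
| 84.8% vs 88.0% | Japanese rates, Protocol 7.3.4 | 56% |
| 50% vs 45% | assumed | 89% |

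At 45% vs 45%, SE = √(2 × 0.2475/225) = 0.0469, so the half-width is 1.96 × 4.69 = 9.2 points. The observed difference must then exceed about −0.8 points. For 80% power, n = (1.96 + 0.8416)² × 0.495/0.01, or 389 per arm.

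**The case against.** On the window, the effect is probably small, and that stands. The scheduled Week 12 sample is taken at the visit where the next supply is dispensed (Protocol Table 3), so it normally precedes the increase. Unscheduled SUA is drawn only when the investigator judges it necessary (Table 3, footnote o). A reader might infer that the Week 12 result is largely a 4 mg result, or materially biased; the documents do not support that. But small size does not make the rule right: it can assign a 4 mg value to a 2 mg label, and it is cheap to repair.

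A practical objection also stands. The protocol defines the date of first dose only for Day 1, and SAP 4.6.1 uses only the overall first and last dose dates, so the first third-period dose date may not be recorded. Dispensing is recorded (Protocol 9.4.10), so a fallback is needed.

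On the objective, the reference-only status is disclosed and identical in protocol and SAP. SAP 4.4.2 prespecifies a stratified difference, its 95% interval, the margin and a per-protocol repeat. Protocol 7.3.3 says assess, not confirm. All of this stands, and only a formal, error-controlled claim is missing. A reader might infer that error control has failed or that a testing sequence is required. Neither follows, because alpha is confined to the primary endpoint. Nor do the low powers above show a design defect: the sample size sections address Week 24 only.

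**Conclusion.** The main point holds. As written, Table 2 lets a sample from the 4 mg period, nominally Days 85 to 98, stand as the 2 mg result and displace a valid earlier value. The affected share is unknown and probably small. The bias of 0.5 to 2.5 points rests on assumed shares of 2% to 10% and assumed rates of 35% and 60%. Its likely direction, towards dotinurad, rests on the protocol's premise that 4 mg brings more subjects to target.

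The secondary point is an inconsistency of wording: three objective lists say *confirm*, and the analysis is reference-only. A fixed-sequence test is an option, not a correction that the documents call for. The Week 24 endpoint, its alpha, power and sample size are not affected.

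**What to change.** **Window (SAP Table 2).** Before unblinding, replace footnote b with wording such as: *In both arms, Week 12 (LOCF) is the latest available post-dose SUA value, from a scheduled or unscheduled visit, taken before the first dose of the third-period supply (if that date was not recorded, on or before the day the supply was dispensed) and no later than Day 98. A subject with no qualifying value is a non-responder.* State that footnote d is subject to this limit for Week 12 (LOCF). Apply the same limit to the observed Week 12 window, which feeds the by-visit summaries and the MMRM.

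The third-period supply exists in both arms, so the limit can be applied blind. Adding *post-dose* is a change in its own right: it stops a baseline value being carried forward. It should hardly move the responder count, since entry requires SUA above 7.0 mg/dL. The cost is a SAP revision approved before unblinding (SAP 2), and a few subjects will use an earlier value. Only the analysis window changes; dosing does not.

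**Objective.** Change *confirm* to *estimate* in the protocol synopsis, Protocol 8.2 and SAP 2.1.2. The protocol edits need a written amendment or administrative change (Protocol 11.1).

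**Option only.** If a formal claim is wanted, test Week 12 non-inferiority after a significant primary result in favour of dotinurad, and conclude it if the lower limit of the stratified two-sided 95% interval exceeds −10 points. This costs no primary alpha. It needs a margin rationale, a stated role for the per-protocol analysis, removal of the reference-only wording, an exemption from the no-adjustment sentences, and a protocol amendment that may need regulatory and IRB/IEC approval. The claim is lost if the primary fails, and power is about 57% at assumed equal rates of 45%.

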#### 4.4.3 Other Efficacy Analyses

No other efficacy analyses are planned for this study.

### 4.5 Pharmacokinetic, Pharmacodynamic, Pharmacogenomic, and Other Biomarker Analyses

Not applicable

#### 4.5.1 Pharmacokinetic Analyses

Not applicable

#### 4.5.2 Pharmacodynamic, Pharmacogenomic, and Other Biomarker Analyses

Not applicable

### 4.6 Safety Analyses

All safety analyses will be performed based on observed data using the Safety Analysis Set. Safety data will be summarized on an “as treated” basis using descriptive statistics or frequency count only. No hypothesis testing will be performed for safety analyses. Study Day 1 for all safety analyses is defined as the date of the first dose of study drug.

#### 4.6.1 Extent of Exposure

The extent of exposure (duration of exposure) to study drug will be summarized using descriptive statistics by treatment group. Duration of exposure of study drug will be defined as the number of days between the date the subject received the first dose of study drug and the date the subject received the last dose of study drug, inclusive.

#### 4.6.2 Adverse Events

The AE verbatim descriptions (investigator terms from the CRF) will be classified into standardized medical terminology using the Medical Dictionary for Regulatory Activities (MedDRA). Adverse events will be coded to the MedDRA (Version 24.1 or higher) lower level term (LLT) closest to the verbatim term. The linked MedDRA preferred term (PT) and primary system organ class (SOC) are also captured in the database.

A treatment-emergent adverse event (TEAE) is defined as an AE that emerges during time from the first dose of study drug to 28 days after the subject's last dose, having been absent at pretreatment or

- Reemerges during treatment, having been present at pretreatment but stopped before treatment, or
- Worsens in severity during treatment relative to the pretreatment state, when the AE is continuous.

Only those AEs that are treatment-emergent will be included in summary tables. All AEs, treatment-emergent or otherwise, will be presented in subject data listings.

An overview table of TEAE, including number of subjects with TEAEs, treatment-related TEAEs, severe TEAEs, SAEs (deaths and other SAEs), TEAEs leading to study drug adjustment (withdrawal, reduced, interrupted) will be provided by treatment group.

In addition, the following summaries will be produced for the TEAEs by treatment group:

- Incidence of TEAEs by PT in descending order
- Incidence of TEAEs by SOC and PT
- Incidence of treatment-related TEAEs by SOC and PT
- Incidence of TEAEs by SOC, PT, and severity
- Incidence of treatment-related TEAEs by SOC, PT, and severity
- Incidence of TEAEs leading to study drug withdrawal by SOC and PT
- Incidence of serious TEAEs by SOC and PT
- Incidence of non-serious TEAEs by SOC and PT
- Incidence of TEAE by PT and time of onset (every 4 weeks)
- Incidence of treatment-related TEAE by PT and time of onset (every 4 weeks)

If a subject experiences more than one TEAE within a preferred term, the subject will be counted only once in the calculation of incidence of TEAE within that preferred term.

Similarly, if a subject experiences more than one TEAE within a SOC, the subject will be counted only once in the calculation of incidence of TEAE within that SOC. If a subject experiences more than one TEAE within a preferred term (or SOC), the occurrence with the

highest severity will be used in the calculation of the incidence of TEAE within that preferred term (SOC) by severity. If a subject experiences more than one TEAE within a preferred term (or SOC), the occurrence considered most closely related to study drug will be used in the calculation of the incidence of TEAE with that preferred term (SOC) by relationship (given by investigator).

In addition, the following TEAEs of interest will be summarized by PT and treatment group.

- Urinary calculi defined by MedDRA HLGT “Urolithiases”
- Liver injury defined by MedDRA SMQ “Hepatic disorders”
- Acute renal failure defined by MedDRA SMQ “Acute renal failure”

TEAEs for the following subgroups will be summarized by SOC, PT and treatment group:

- SUA level category (<9; 9 to <10; 10 to <11;  $\geq$ 11 mg/dL)
- BMI category (<25;  $\geq$ 25 kg/m^2)
- Classification of hyperuricemia (overproduction type, underexcretion type, combined type, other type)

A subject data listing of all AEs, all AEs leading to death, all SAEs and all AEs leading to discontinuation from study drug will be provided.

#### 4.6.3 Laboratory Values

Laboratory results will be summarized using Système International (SI) units, as appropriate. For all quantitative parameters listed in protocol Section 9.5.1.4.4, the actual value and the change from baseline to each postbaseline visit will be summarized by visit and treatment group using descriptive statistics. Qualitative parameters listed in protocol Section 9.5.1.4.4 will be summarized using frequencies (number and percentage of subjects), and changes from baseline to each postbaseline visit will be reported using shift tables. Percentages will be based on the number of subjects with both nonmissing baseline and relevant postbaseline results.

Laboratory test results will be assigned a low/normal/high (LNH) classification according to whether the value was below (L), within (N), or above (H) the laboratory parameter's reference range. Within-treatment comparisons for each laboratory parameter will be based on 3-by-3 tables (shift tables) that compare the baseline LNH classification to the LNH classification at each postbaseline visit. Similar shift tables will also compare the baseline LNH classification to the LNH classification for the highest and lowest value.

[Appendix 1](#) (Sponsor's Grading for Laboratory Values) presents the criteria that will be used to identify subjects with treatment-emergent markedly abnormal laboratory values (TEMAVs). A TEMA V is defined as a postbaseline value with an increase from baseline to a grade of 2 or higher. When displaying the incidence of TEMA Vs, each subject may be counted once in the laboratory parameter high and in the laboratory parameter low categories, as applicable.

The number (percentage) of subjects with TEMA V (markedly abnormal high/low) will be summarized by treatment group.

The number (percentage) of subjects who met the following criteria for the hepatic test at the same time will be summarized by treatment group. If a subject met the criteria more than once for available laboratory data, the subject will be counted only once in the calculation of the incidence.

- Elevated AST or ALT lab value that is greater than or equal to  $3 \times$  ULN
- Elevated total bilirubin lab value that is greater than or equal to  $2 \times$  ULN
- Alkaline phosphatase lab value that is less than  $2 \times$  ULN

A subject data listing of laboratory values will be provided.

